### B1. PURPOSE OF PROTOCOL

The purpose of the protocol is to test the hypothesis that elimination of the use of non-depolarizing neuromuscular blocking agents (NMBA) for maintenance of general anesthesia in patients at high risk of developing postoperative pulmonary complications (PPCs) undergoing non-cardiac operations is associated with reduced risk of PPCs.

*Specific Aim 1:* To test the primary hypothesis that avoidance of non-depolarizing NMBAs, as compared to standard care which includes the use of non-depolarizing NMBAs, is associated with a lower risk of a composite of PPCs (including respiratory failure, suspected respiratory infection, aspiration pneumonia or pneumonitis, atelectasis, bronchospasm and reintubation within 28 days of index operative procedure) and all cause in-hospital mortality both within 28 days of index operative procedure.

*Specific Aim 2:* To test the key-secondary hypothesis that avoidance of non-depolarizing NMBA, compared to standard care which includes the use of non-depolarizing NMBA, is associated with higher vasopressor equivalent dose, which may be the consequence of higher dosing of opioids and anesthetics. Further, we shall also evaluate the following secondary endpoints: duration of intraoperative hypotension (defined as mean arterial pressure <55mmHg), surgeon's assessment of surgical field, cost of anesthetic medications, time to PACU discharge readiness (interval between arrival and time when meeting PACU discharge criteria), rate of unplanned ICU admissions or return to operating room within 24 hours, hospital length of stay and 30-day readmission rates.

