### Study Endpoints:

1. Primary Endpoint: Composite of postoperative pulmonary complications (respiratory failure, suspected respiratory infection, aspiration pneumonia or pneumonitis, atelectasis, bronchospasm and reintubation) and all cause in-hospital mortality both within 28 days of index operative procedure
2. Secondary endpoint (safety):
  - a. Vasopressor use between groups,
  - b. Duration of intraoperative hypotension (defined as mean arterial pressure <55mmHg),
  - c. Surgeon's assessment of surgical field.
3. Other end points:
  - a. Time to post-anesthesia care unit (PACU) discharge readiness,
  - b. Cost of anesthetic medication,
  - c. Rate of unplanned ICU admission or return to operating room within 24 hours,
  - d. Hospital length of stay
  - e. 30-day readmission rates.

The following baseline variables will also be collected: Clinical and demographic variables will be collected including age, gender, body mass index, type and severity of chronic lung disease, ASA class, obstructive sleep apnea, use of CPAP/Bipap, smoking history, hypertension, coronary artery disease, heart failure, cerebrovascular accident or neurologic dysfunction, history of aspiration, use of home oxygen, chronic kidney disease, diabetes mellitus, Charlson comorbidity index and Procedural Severity Score. Additionally, to track other important intraoperative and postoperative

factors related to overall patient outcome and protocol adherence, we will record administrative, demographic, clinical and billing data including:

- Vital Signs
- Medications administered
- Ventilator settings
- Urine output
- End tidal carbon dioxide concentration
- Dead space ventilation
- Alveolar-Arterial oxygen gradient
- Blood transfusion history
- Length of operation
- Type of operation

*Assessment of Primary Outcome:*

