Detection of postoperative pulmonary complications and in-hospital mortality would be achieved by close review of the patient's medical records during the hospital stay, for a maximum of 28 days. Study team members blinded to the treatment assignment will review clinician/ nursing/ respiratory therapy notes, laboratory/ imaging data and communicate with the clinical team as needed. Attending surgeons would be asked to rate overall operating conditions at the end of the procedure on a numerical scale modified from an earlier study. To ensure blinding of assessors, printed anesthetic records will be placed in a sealed envelope and attached to the patient's chart after formal hand-off to nursing staff. Members of the clinical team will continue to have access to the anesthesia record through the electronic health record without restriction for the provision of clinical care.

*Adverse Event Reporting:*

We will assess for adverse events during the intraoperative period, as well as for the first 48 hours post-surgery.

Patients in this study are being randomized to anesthetic protocols that are both considered within the standard of care. We will adhere to the CCI post approval reporting requirements with regard to Adverse Events that are related, serious, and unexpected.

We will track the following pre-specified events as part of clinical outcome assessment. If any are deemed possibly related to study participation, they will be reported to the IRB in accordance with the reporting guidelines.

- Significant intraoperative hypoxemia
- Severe patient ventilator dyssynchrony
- Inability to ventilate
- Pneumothorax

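### Adverse events are assessed only to 48 hours, so later non-fatal, non-pulmonary serious events and later reoperations are not systematically collected by arm, although in-hospital charts are already reviewed for up to 28 days

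*Combined protocol and SAP*

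**What the plan says.** Under Adverse Event Reporting, the protocol states: "We will assess for adverse events during the intraoperative period, as well as for the first 48 hours post-surgery". No reason is given for 48 hours. The section then lists four events to be tracked: hypoxemia, ventilator dyssynchrony, inability to ventilate, and pneumothorax. It also commits to the review board's reporting rules for events that are at once related, serious and unexpected, with no time limit stated.

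Under Assessment of Primary Outcome, pulmonary complications and in-hospital death are found by "close review of the patient's medical records during the hospital stay, for a maximum of 28 days". Blinded study staff "will review clinician/ nursing/ respiratory therapy notes, laboratory/ imaging data and communicate with the clinical team as needed".

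Specific Aim 2 (section B1) hypothesises that avoiding relaxants "is associated with higher vasopressor equivalent dose, which may be the consequence of higher dosing of opioids and anesthetics". Study Endpoints names three secondary safety endpoints: vasopressor use, duration of intraoperative mean arterial pressure below 55 mmHg, and the surgeon's rating of the field. Among the other endpoints are length of stay, 30-day readmission and "Rate of unplanned ICU admission or return to operating room within 24 hours".

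Sections B4 and B5 say the results will compare the two techniques on safety as well as efficacy and will inform a larger trial.

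**The concern.** The protocol itself names the routes by which avoiding relaxants might do harm: more anesthetic, opioid and vasopressor (Specific Aim 2), and a harder operating field (section B5). Its safety endpoints measure those routes, not what follows for the patient. Hypotension is measured during the operation, the field is rated at its end, and vasopressor use is a measure of treatment.

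Whether either route leads to kidney injury, a cardiac event, a stroke or a reoperation depends on adverse-event recording, and that stops at 48 hours. Baseline chronic kidney disease, coronary disease and cerebrovascular accident are recorded, but no postoperative outcome corresponds to them. At stake is whether the trial can describe the safety comparison it promises and give a later trial any estimate of such events.

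**Working it through.** The question is mainly one of coverage, so the first step sets the stated windows side by side.

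**1. Windows (Study Endpoints and Adverse Event Reporting)**

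| Item | Window | Shows a late non-fatal, non-pulmonary event by type and arm? |
|---|---|---|
| Adverse-event assessment | Surgery plus 48 hours | No, ends too early |
| Return to operating room, unplanned ICU admission | 24 hours | No, ends too early |
| Pulmonary complications, in-hospital death | In hospital, at most 28 days | No, other event types |
| Length of stay | Whole stay | Indirectly, without cause |
| Readmission | 30 days | Indirectly, without cause |
| Four tracked events | None stated | No, all respiratory or ventilatory |
| Related, serious and unexpected events | None stated | Only if all three conditions are met; a reporting duty |
| Case report form fields for unanticipated problems, including adverse events (section B9) | None stated | Serve notification of the lead site; no tabulation planned |

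The Data Analysis paragraph does not mention adverse events. A return to the operating room between 24 and 48 hours might be logged as an adverse event but lies outside the endpoint; after 48 hours neither applies.

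**2. Length of the gap.** 48 hours = 2 days. The chart review is capped at 28 days, so at most 28 − 2 = 26 in-hospital days are read for pulmonary events and death but not for other adverse events. The actual number is smaller for anyone discharged earlier, and the documents give no length of stay.

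**3. The plan's sample size.** For 40% versus 15%, two-sided alpha 0.05 and 80% power, with p̄ = 0.275:

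n = [1.960·√(2·0.275·0.725) + 0.842·√(0.40·0.60 + 0.15·0.85)]² / 0.25² = (1.238 + 0.510)² / 0.0625 ≈ 48.9, so 49 per group.

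The plan says at least 50, which reproduces; power at 50 is 80.9%. Longer recording of adverse events enters none of these terms.

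**4. What the added data could show with 50 per arm.** The documents give no late event rates, so the rates here are assumptions.

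Chance of at least one event in an arm = 1 − (1 − p)^50:
- p = 2%: 64%
- p = 5%: 92%
- p = 10%: 99.5%

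Power of a two-sided 0.05 comparison of the arms:
- 5% versus 10%: 15% (435 per arm would be needed for 80%)
- 10% versus 20%: 29%
- 5% versus 20%: 62%

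The data would therefore reveal whether such events occur and of what type, but would not support a test between arms.

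**The case against.** The best defence is that this is a 100-patient pilot of two techniques already accepted as standard care, with safety results labelled exploratory. Serious late harm is not ignored: in-hospital death and pulmonary events are counted to 28 days, and stay and readmission may also reflect it. Related, serious, unexpected events must be reported whenever they occur, and the case report form has fields for adverse events. With about 15% power for a doubling from 5% to 10%, more data would settle nothing.

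Much of this stands, and it rules out several stronger readings.

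- A reader might infer that the trial expects more hypotension without relaxants. It hypothesises a higher vasopressor dose; hypotension duration is evaluated with no stated direction.
- A reader might infer that benefit is followed for 28 days and harm for two. The composite is tested two-sided, so an excess of pulmonary events or deaths without relaxants would count as harm over the same 28 days.
- A reader might infer that the short window biases the trial towards equal safety. The window is the same in both arms, and no equivalence or non-inferiority test of safety is planned.
- A reader might assume that organ injury usually appears after 48 hours, or express two days as a share of 28. The documents give no timing of such events, and 28 days is a cap on an unstated length of stay.

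What the defence does not answer is identification. Death, stay and readmission do not separate a non-fatal kidney injury or a day-4 reoperation from any other cause. The reporting duty passes only events meeting all three conditions, so it is not a count by arm. Low power argues against a test, not against a table.

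**Conclusion.** The concern holds in a limited form. Non-fatal, non-pulmonary serious events first recognised after 48 hours, and returns to the operating room outside the 24-hour endpoint, are not systematically collected by arm. The gap is at most 26 in-hospital days per patient, and less with earlier discharge. The number of events missed cannot be derived from the documents.

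This does not affect the primary analysis, the sample size or the error rate, and it does not show that the safety comparison is biased. It leaves the stated aim of comparing safety thinner than it need be, when the relevant notes and laboratory results are already being read. The change is worth making. The conclusion assumes that some patients remain in hospital beyond 48 hours, which is plausible because only high-risk patients are enrolled and ambulatory surgery is excluded.

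**What to change.** In Adverse Event Reporting, extend recording of postoperative serious adverse events, naming renal, cardiac, neurological and surgical events as examples, and of any return to the operating room, to discharge or day 28, whichever is first. Do this within the existing blinded chart review. In Data Analysis, state that these will be tabulated descriptively by arm, without a test.

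Keep intraoperative events in the current adverse-event process, outside the blinded review. The protocol seals the printed anesthetic record to keep outcome assessors blinded, and recording intraoperative events in their review would undermine that. Keep the 48-hour window for non-serious events.

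The cost is some extra data entry. No added visit is needed, and sample size, alpha and power are unchanged. Two limits remain: the figures will be descriptive at 50 per arm, and events after discharge will still appear only as readmissions.

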**Collaboration with MGH**

This randomized control trial is planned in collaboration with MGH. We plan to recruit patients in parallel at the two institutions (BIDMC and MGH) and implement the study protocol after obtaining institutional approval. [name] [name] shall be the site PI at MGH and work in collaboration with [name], PI at BIDMC. A research coordinator credentialed at MGH will work under the guidance of [name] to follow study protocol at MGH. Similarly, a study coordinator will work with [name] to follow protocol at BIDMC. Postoperative follow-up will be conducted by research staff credentialed at respective institutions through review of electronic medical records and in-person patient visits as appropriate for ascertaining components of PPC. Please see section B9 for more details on the collaboration.

## 1. STATISTICAL CONSIDERATIONS

- a. **Sample Size Justification:** Assuming the incidence of PPC to be 40% and 15% in Groups C and NR, respectively, we estimated that we would need at least 50 patients in each group to achieve a two-sided  $\alpha = 0.05$  and 80% power. Although the effect size in this assumption is high, if a difference of this magnitude is observed, the study will be well-powered. However, due to the scant knowledge about the directionality of the effect that we are exploring, observing even a smaller difference in this preliminary study will be useful in estimating a reliable effect size that can be used in designing a larger, more definitive study in the future. Results from our secondary endpoints will provide valuable exploratory data on the safety and efficacy of maintenance of general anesthesia without non-depolarizing NMBA.
- b. **Data Analysis:** Descriptive statistics will be assessed and presented as mean( $\pm$ -SD), median(IQR) or frequencies and proportion depending on type and distribution. Differences between groups in continuous variables will be compared using parametric or non-parametric tests as appropriate. Categorical data including the primary outcome (composite of PPC and all cause 28 day in-hospital mortality) will be compared with Chi-square or Fisher's exact test as appropriate. Two-sided p-value of less than 0.05 will be considered significant for all analyses. Logistic regression will be used to assess the relationship between the composite outcome and use or avoidance of non-depolarizing NMBA. Data will be presented as odds ratio and 95% confidence intervals. Individual outcomes will be reported to demonstrate potential trends between the two groups. Continuous outcome variables will be compared between treatment groups using t-test or Wilcoxon rank sum test as appropriate. Exploratory sensitivity analyses will be conducted to analyze if treatment effects were moderated by study site, surgical site or preoperative risk score after adjusting for patient and procedural risk factors such as Charlson comorbidity index and Procedural Severity Score. Statistical consultation shall be provided by [name], PhD at MGH. Statisticians will be blinded to group assignment.

Statistical analysis will be performed at BIDMC by experienced local study staff in collaboration with biostatisticians under the guidance of [name] (MGH). We shall establish a Data Use Agreement with MGH to facilitate exchange of de-identified study related data between the two study sites.

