### B3. DESCRIPTION OF RESEARCH PROTOCOL

#### A. STUDY DESIGN – OVERVIEW, METHODS, PROCEDURES

##### Experimental design and methods

**Study Design**

Pragmatic prospective randomized controlled assessor-blinded effect-size finding trial at two academic tertiary care hospitals: Beth Israel Deaconess Medical Center (BIDMC) and Massachusetts General Hospital (MGH).

Prior to randomization, if subjects are eligible on the basis of inclusion and exclusion criteria, informed consent will be obtained from the participants. Once informed consent is obtained, patients will be randomized in a 1:1-ratio to one of two study arms: standard care non-depolarizing NMBA use (**C**) versus avoidance of non-depolarizing NMBA (**NR**) by computer-generated variable block size random allocation stratified a) study site (MGH or BIDMC) and b) expected preoperative risk of PPC (<40% and ≥40%) as predicted by expanded risk stratification tool as defined above (**Table 1**). Since blinding to use of NMBA is unfeasible, anesthesia team members would be aware of group assignment.

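### The primary comparison leaves out site and preoperative risk, although randomisation is stratified on both: a valid test, but a small and cheap improvement is missed

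*Combined protocol and SAP*

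**What the plan says.** Section B3, Study Design, describes "computer-generated variable block size random allocation stratified a) study site (MGH or BIDMC) and b) expected preoperative risk of PPC", with the risk factor cut at a predicted 40%. That gives four strata: two sites by two risk levels.

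Section 1, Statistical Considerations, b. Data Analysis, handles the primary outcome in three steps:

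- **Test.** "Categorical data including the primary outcome (composite of PPC and all cause 28 day in-hospital mortality) will be compared with Chi-square" or Fisher's exact test, whichever is judged appropriate. No stratification is mentioned.
- **Model.** A logistic regression relates the composite to use or avoidance of the agents. No covariates are listed, and "Data will be presented as odds ratio and 95% confidence intervals".
- **Exploratory work.** Site, surgical site and preoperative risk score are examined as possible effect modifiers, adjusted for factors such as the Charlson index and the Procedural Severity Score.

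Nowhere do the two stratification factors enter the primary test or the main logistic model.

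**The concern.** Site and predicted risk were thought important enough to constrain the allocation, and every patient has a risk score before randomisation. A primary comparison that pools over both leaves prognostic information unused. With about 50 patients per arm and planned power close to 80%, even a few points of power are worth having when they need no new data.

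The second part concerns the effect measure. The Study Design section presents the trial as one that looks for an effect size, and the sample-size paragraph says the result should help design a larger study. That later calculation needs the two absolute risks and their difference. At a control risk of 40%, an odds ratio alone is easily misread as a risk ratio.

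**Working it through.** **1. The plan's own figure.** Inputs from section 1, a: "Assuming the incidence of PPC to be 40% and 15% in Groups C and NR, respectively", two-sided 0.05, 80% power, equal allocation. With pooled variance and mean risk 0.275:

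n = [1.96 × √(2 × 0.275 × 0.725) + 0.842 × √(0.40 × 0.60 + 0.15 × 0.85)]² / 0.25² ≈ 49 per group.

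The stated 50 per group is reproduced, and the formula gives 80.9% power at 50. Exact power at 50 per group is 81.9% for the uncorrected chi-square and 75.8% for Fisher's exact test.

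**2. How many patients fall below the 40% cut.** Section 2 requires a score of at least 20. Table 1 gives 35.4% at score 20 and 68.2% at score 25. On the logit scale the slope is

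[ln(0.682/0.318) − ln(0.354/0.646)] / 5 = [0.763 − (−0.602)] / 5 ≈ 0.273 per point.

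Score 21 then corresponds to about 41.9%, so only a score of exactly 20 lies in the low stratum. High-risk surgery (13) plus inpatient surgery (11) already gives 24, about 62%, and ambulatory surgery is excluded. In Table 2, the 30–40% band holds 288 of the 288 + 215 + 2,567 = 3,070 patients at 30% or above, or 9.4%. Of 100 patients that is about 9, spread over two sites and two arms: roughly 2 per cell.

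**3. Stratifying the test by the randomised strata.** Simulation: 100 patients, stratified blocks, 40,000 trials per scenario, marginal risks 40% and 15% (40% in both arms for type I error). Assumed: sites equal in size, 5% or 9.4% of patients in the low stratum, risk odds ratio 1.5–8, site odds ratio 1–1.5.

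| | Pooled chi-square | Cochran-Mantel-Haenszel |
|---|---|---|
| Power | 81.9–82.6% | 81.6–82.8% |
| Type I error | 4.9–5.5% | 4.8–5.3% |

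The difference in power runs from about -0.5 to +0.6 points. Further runs with other assumptions widen this to about -0.7 to +0.7. A gain of a full point appeared only when 30–50% of patients were assumed to be in the low stratum and the risk odds ratio was about 3–4 or more. Step 2 does not point to a stratum of that size.

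**4. Adjusting for the continuous score and site.** This does not depend on the 40% cut. It does need assumed prevalences for the score items, because the documents give none.

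- With the Table 1 slope, a score standard deviation of 2.5 points and a site log odds ratio of 0–0.8 (4,000 trials per scenario), power was 81.6–82.9% for the pooled chi-square and 85.0–86.2% for the adjusted likelihood-ratio test, a gain of about 3.5 points. Type I error was 4.8–5.5% and 5.1–5.6%.
- With slopes from half to all of that (0.137–0.273 per point), the gain was about 1–5 points, but the likelihood-ratio type I error was 5.1–6.3%, so part of the upper end is not real power.
- A further run found about 0.5–4 points with adjusted type I error 4.3–5.5%. I take this as the working range.

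The model is affordable: expected events are 0.40 × 50 + 0.15 × 50 = 27.5, for three coefficients (arm, site, score).

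**5. Effect measures at the planned rates.**

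- Odds ratio: (0.15/0.85) / (0.40/0.60) = 0.265
- Risk ratio: 0.15/0.40 = 0.375
- Risk difference: 40 − 15 = 25 points

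Read as a risk ratio, 0.265 suggests a reduction of about 73%. The planned relative reduction is 62.5%.

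**The case against.** The strongest reply is that nothing is broken. A pooled test after stratified randomisation is valid; leaving out prognostic strata makes it conservative if anything. For a preliminary two-site trial a simple test is defensible. That stands, and it limits the point to an improvement.

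Several stronger readings are tempting, and the documents do not support them:

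- **That the plan ignores its design.** Site and risk score are named in the exploratory analyses. Only the primary test and main model leave them out.
- **That the pooled test is markedly conservative or short of power.** This would need a low-risk stratum of substantial size. At the share Table 2 suggests, type I error stays at about 4–6% and stratifying gains almost nothing.
- **That the score's AUROC of 0.84 promises a large gain.** That figure comes from all non-cardiac intubated patients, with a 12.2% event rate. It cannot be carried over to patients selected for a score of at least 20.
- **That adjustment narrows the odds-ratio interval.** In logistic regression the adjusted odds ratio is a conditional quantity. The benefit is in power, not in a shorter interval for the log odds ratio.
- **That absolute risks will be missing.** Frequencies and proportions are to be reported, so a reader could derive the risk difference. What the plan does not name is that measure with its interval.

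It is also fair to say that the choice between chi-square and Fisher (81.9% against 75.8%) matters more than stratification. At the planned rates the expected events per arm are 0.275 × 50 = 13.75, so the usual rule would select the chi-square, but the plan does not state the rule.

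**Conclusion.** The point holds in a modest form. The primary test and the main model omit both stratification factors, and the only named effect measure is ill suited to planning the next trial. Adjusting for the continuous score and site is worth about 0.5–4 power points at 40% versus 15% with 100 patients; stratifying by the 40% cut is worth essentially nothing.

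The range rests on assumed item prevalences, a common conditional odds ratio, no dropout, and the score's predictive strength among eligible patients. That strength is the main unknown. The score was built for a composite that included pleural effusion and pneumothorax but not death, and the planned 40% control risk is below the 62% that Table 1 implies at score 24. The 9.4% share is also approximate: Table 2 may use the narrower definition of high-risk surgery, and physician review of the record plays a part in eligibility.

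**What to change.** In section 1, b:

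- Make the primary analysis a logistic regression of the composite on randomised arm, with site and the continuous preoperative score as covariates. Name the test to be used (for example likelihood ratio). Referring to the randomised arm also removes any doubt about patients in the no-relaxant arm who receive rescue.
- Report the risk difference and risk ratio with 95% confidence intervals beside the odds ratio, and state how they are obtained.
- Keep the unadjusted chi-square as a supportive analysis. Naming one primary analysis also closes the open choice between chi-square and Fisher.
- If a Mantel-Haenszel analysis is preferred, stratify by site and pool the near-empty stratum below 40%.

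The cost is a few sentences and no new data. The small downside is a conditional odds ratio that is slightly harder to explain; the risk difference beside it largely offsets that.

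### For sparse safety endpoints, naming Boschloo's exact test instead of Fisher's would recover some power at almost no cost; this is an efficiency gain, not an error in the plan

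*Combined protocol and SAP*

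**What the plan says.** Section 1.b, Data Analysis, states that categorical data, the primary composite among them, "will be compared with Chi-square or Fisher's exact test as appropriate". It gives no criterion for choosing between the two tests and names no other exact test. The threshold is set once: "Two-sided p-value of less than 0.05 will be considered significant for all analyses".

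The binary endpoints other than the primary include "Rate of unplanned ICU admission or return to operating room within 24 hours", placed among the other end points in the Study Endpoints list, and the single components of the composite: "Individual outcomes will be reported to demonstrate potential trends between the two groups". No expected rate and no power are given for any of them. Section 1.a describes their status: "Results from our secondary endpoints will provide valuable exploratory data on the safety and efficacy".

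The sample size (section 1.a) is "at least 50 patients in each group", under this premise: "Assuming the incidence of PPC to be 40% and 15% in Groups C and NR, respectively". Under Study Design, "patients will be randomized in a 1:1-ratio".

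**The concern.** Fisher's test conditions on both margins of the 2x2 table. When events are few, very few tables are possible, and the test rejects well below its nominal level. In a trial of 100 patients this falls on the rare endpoints, where harm from avoiding relaxants might appear: reintubation, aspiration, an unplanned ICU stay, a return to theatre. A conservative test tilts these towards no significant difference. The trial is meant to inform the relative safety of the two techniques and the design of a larger study (sections B4 and B5). Another exact test keeps the same 5% ceiling and is never less powerful than Fisher's, so part of the loss can be avoided.

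**Working it through.** **Inputs.** From the documents: 50 per arm, 1:1, two-sided 0.05, primary rates 40% and 15%. Assumed: the expected-count rule as the meaning of the plan's unspecified choice, and the event rates for the sparse endpoints.

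**The plan's own figure.** With pooled variance and no continuity correction, mean rate 0.275:

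n = [1.96·√(2·0.275·0.725) + 0.8416·√(0.4·0.6 + 0.15·0.85)]² / 0.25² = (1.238 + 0.510)² / 0.0625 ≈ 48.9, so 49 per arm.

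The stated minimum of 50 is reproduced.

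**When Fisher's test is chosen.** With equal arms, the expected number of events per arm is half the total. An expected count below 5 therefore means fewer than 10 events in 100 patients. At the planned rates, 0.40·50 + 0.15·50 = 27.5 patients have the composite, which consists of six complications and death. One patient can have several components, so this makes some sparse components likely but does not prove it for any one of them.

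**Two example tables, by hand.** With equal arms, the two-sided Fisher p is twice the one-sided tail.

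- 5 vs 0 events: 2·C(50,5)/C(100,5) = 2·2,118,760/75,287,520 = 0.056.
- 7 vs 1 events: 2·[C(50,8) + 50·C(50,7)]/C(100,8) = 2·5,531,098,650/186,087,894,300 = 0.059.

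Boschloo's test uses the Fisher p-value as its statistic and takes the largest rejection probability over all common event rates. At 50 per arm it rejects when the Fisher p is at most 0.0693, with a maximum size of 4.87% (reached near a 40% event rate). Its p-values for these tables are 0.035 and 0.037. Both cross 0.05; neither does under Fisher's test.

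**True size.** All 51 x 51 tables were enumerated, and for each common rate the binomial probabilities of the rejected tables were summed:

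| Common event rate | Chance of fewer than 10 events | Plan under the expected-count rule | Fisher in every table | Boschloo in every table |
|---|---|---|---|---|
| 3% | 99.9% | 0.18% | 0.17% | 0.8% |
| 5% | 97.2% | 0.9% | 0.72% | 2.1% |
| 7% | 83.8% | 2.1% | 1.26% | 2.9% |
| 10% | 45.1% | 4.1% | 1.79% | 3.2% |

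The plan's size rises at 10% because more than half of such trials then have 10 or more events and go to chi-square.

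**Power.** Chi-square is used at 10 or more events in both columns; only the test in the sparse tables differs:

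| True rates | Fisher if sparse | Boschloo if sparse |
|---|---|---|
| 2% vs 10% | 21.0% | 31.7% |
| 2% vs 12% | 34.8% | 46.3% |
| 0% vs 10% | 38.4% | 56.9% |
| 2% vs 6% | 3% | 8% |
| 3% vs 8% | 7% | 13% |

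The third row can be checked directly. With no events in one arm, Fisher's test needs at least 6 in the other and Boschloo's at least 5. For X ~ Bin(50, 0.10), P(X≥6) = 0.384 and P(X≥5) = 0.569.

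**Size of the whole procedure.** With Boschloo's test in sparse tables and uncorrected chi-square elsewhere, the size is 5.3% at a 12% rate and 5.5% at 15%, with a maximum of about 5.7%. The plan's current combination has the same maximum, because it comes from the chi-square part.

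**Primary endpoint.** At 40% vs 15%, the chance of fewer than 10 events in total is about 2 in a million. The rule therefore selects chi-square, whose exact power at 50 per arm is 81.9%.

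**The case against.** The case for leaving the text alone is substantial.

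- Fisher's test for sparse tables is standard practice, and 5% is a ceiling that it respects. This stands: a reader might infer an error-rate mistake, and there is none.
- Much of the gap is discreteness that any exact test shares. This stands: Boschloo's own size is only 0.8%, 2.1% and 3.2% at rates of 3%, 5% and 10%. Its 4.9% maximum is not what it delivers for rare events.
- No power is claimed for these endpoints and the plan calls the secondary results exploratory. This also stands, and it limits how much the point matters. It does not remove it, since the 0.05 threshold is declared for all analyses and the results are meant to speak to safety.
- The gain is small when the true difference is modest (3% to 8% for 2% vs 6%). With 100 patients, sample size is the main limit under any test.

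Two stronger readings are tempting. One is that every sparse endpoint is tested at a true level of 0.2% to 2%. That would hold for rates of about 3% to 12% if Fisher's test were used in every table. Under the expected-count rule it holds only for about 3% to 7%, and the documents give no rates that place any endpoint there. The other is that the primary loses its 80% power, because the same sentence allows Fisher's test for it and Fisher's power at 40% vs 15% is 75.8%. The expected-count rule does not lead to Fisher's test at those rates, so the stated power is delivered.

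**Conclusion.** The point holds as a cheap improvement to exploratory safety analyses. For endpoints with event rates of about 3% to 7%, the plan's procedure works at a true level of roughly 0.2% to 2%. Using Boschloo's test in the sparse tables adds about 11 to 19 percentage points of power for large differences (2% vs 10%, 2% vs 12%, 0% vs 10%) and about 5 or 6 for modest ones (2% vs 6%, 3% vs 8%). It leaves the worst-case size of the whole procedure unchanged at about 5.7%.

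This rests on exactly 50 per arm, on the expected-count rule as the reading of the plan's open choice, and on assumed event rates. The documents do not support calling the plan invalid, saying that the test choice is the main reason harm could be missed, or doubting the power stated for the primary.

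**What to change.** In section 1.b, after the sentence on categorical data, add in substance: for secondary and other binary endpoints and for single components of the composite, when any expected cell count is below 5, Boschloo's unconditional exact test (two-sided) replaces Fisher's exact test; otherwise the uncorrected chi-square test is used. This also supplies the selection rule that the section lacks. The primary analysis needs no change on this account.

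The cost is one sentence. The test is available in free software (scipy, for example), and no further data or patients are needed. The drawback is that readers know the test less well than Fisher's, so a short explanation in the report would help. The plan should not claim that the combined procedure is capped at 5%: that holds for Boschloo's test itself (at most 4.9%), not for its combination with chi-square.
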